## 6) Inclusion and Exclusion Criteria

Individuals with AUD who are seeking treatment to reduce their drinking (N=40) will be recruited from the community through advertisements placed in local newspapers, radio stations, movie theatres, online forums, and flyers, word of mouth, and email communications directed towards community support groups.

### Inclusion Criteria

- 1) males and females age 18-60 meeting DSM-V criteria for moderate or severe AUD in the past year
- 2) interested in cutting down or quitting drinking
- 3) able to provide voluntary informed consent
- 4) have at least 4 heavy drinking days ( $\geq 5$  drinks per day for men, and 4 for women) in the past 30 days

### Exclusion Criteria

- 1) severe liver disease; severe kidney disease; gallbladder disease or gallstones
- 2) chronic renal or hepatic failure
- 3) recent pancreatitis
- 4) insulin-dependent diabetes
- 5) other urgent medical problems
- 6) moderately elevated liver function tests (AST or ALT greater than 2 times upper limit of normal) or elevated creatine kinase (CK)
- 7) schizophrenia, schizoaffective disorder, Bipolar I disorder, suicidal thoughts in the last month
- 8) current moderate or severe other substance use disorder (SUD; except nicotine or marijuana)
- 9) active legal problems with the potential to result in incarceration
- 10) pregnancy or lactation, or child bearing age and not on birth control or not willing to use other birth control methods (e.g. condoms)
- 11) current daily use of anti-craving medications, mood stabilizers, benzodiazepines, or anti-psychotics
- 12) regularly taking a medication contraindicated for use with gemfibrozil including other fibrates, statins, repaglinide, or which are believed to interact with gemfibrozil such as dasabuvir, dabrafenib, loperamide, montelukast, paclitaxel, pioglitazone, rosiglitazone, colestipol, colchicine and warfarin
- 13) a history of alcohol withdrawal-induced seizures or delirium tremens (hallucinations, disorientation) requiring hospital admission during the last ten years
- 14) a history of moderate or severe traumatic brain injury (TBI; loss of consciousness  $>30$  minutes)
- 15) left-handedness
- 16) any contraindications for MRI

## 7) Multi-Site Research

N/A

## 8) Study Timelines

Individual participant's involvement will last ~15 hours over 6 weeks, which includes 4 weeks of medication/placebo. We anticipate ongoing enrollment of participants for approximately 12 months.

## 9) Study Endpoints

The study will close enrollment once 20 participants have been randomized. Based on previous medication trials for AUDs, we expect ~70-80% of participants will complete at least two weeks of the medication, which will be sufficient for deriving initial effect size estimates.

## 10) Study Methods

Participants will be asked to complete the following procedures:

### Screening visit

After the participant has reviewed and signed the consent form, breath alcohol will be measured (<.01 required), participants will complete a 90 day timeline follow-back (TLFB) to establish adequate drinking levels for inclusion, a handedness questionnaire, and a MRI safety screener to assess eligibility. In addition, participants will be interviewed using portions of the Structured Clinical Interview (SCID) for Psychotic, Anxiety, Mood, and Drug and Alcohol Use Disorders to establish whether they have moderate to severe AUD and/or exclusionary SUD and psychiatric disorders. In addition, all participants will complete a urine drug screen and female participants will complete a urine pregnancy test. In addition, trained research staff will conduct a blood draw to obtain baseline levels of CBC, LFT's, BMP, triglycerides, GGT, and CK. Expected time: 2 hours

### Medical history visit

If participants are eligible based on the screening visit, a subsequent visit will be scheduled for the study physician to conduct a physical examination and medical history. If not already completed at the screening visit (visit 1), trained research staff will conduct a blood draw to obtain baseline levels of CBC, LFT's, BMP, triglycerides, GGT, and CK. Expected time: 2 hours

### Baseline visit

Participants who are deemed medically eligible for the study will be scheduled for a baseline appointment during which participants will complete assessments, a baseline MRI session, and the first motivational enhancement therapy (MET) session and will receive medication along with instructions for taking the medication. Expected time: Assessments (2.5 hours), MRI (1 hour), MET session (.5 hours), medication dispensing/instructions (.5 hours)

Baseline Assessments. We will collect measures of craving (Penn Alcohol Craving Scale (PACS), impaired control over drinking (Impaired Control Scale), alcohol dependence severity (Alcohol Dependence Scale), nicotine dependence (Fagerstrom Test for Nicotine Dependence), hazardous drinking (AUDIT), intelligence (WTAR^99), emotional regulation (Difficulties in Emotion Regulation Scale (DERS), State Difficulties in Emotion Regulation Scale (S-DERS), and Emotion Regulation Questionnaire (ERQ)), treatment alliance (obtained at the end of each therapy session), motivation (Stages of Change Readiness and Treatment Eagerness Scale(SOCRATES)) and outside treatment-seeking (Treatment Services Review). In addition, we will collect a demographics form and a locator form to facilitate tracking of

participants. Withdrawal will be measured using the Clinical Institute Withdrawal Assessment for Alcohol (CIWA); if participants are experiencing clinically significant active alcohol withdrawal (CIWA>8), they will be asked to have their withdrawal treated before returning to initiate treatment. The Digit Span test will be used to measure working memory. To measure tendency to discount future rewards, we will use the Monetary Choice Questionnaire (MCQ) which presents participants with choices between immediate rewards and larger, delayed rewards (e.g. \$10 today vs. \$27 in two weeks). Depression, anxiety, and anger will be measured using the PROMIS measures of these constructs. The Drinker Inventory of Consequences (DrInC) will be administered to assess negative consequences from drinking; the results from this questionnaire will be used in the MET sessions. Finally, participants will complete a urine drug screen (all participants) and pregnancy test (females only).

An emotional working memory task will be used to assess working memory in the presence of emotional distractors (Marx et al, 2014). In the task, participants are instructed to remember letters that are superimposed onto negative, neutral, or positive pictures and judge whether the current letter matches the letter 1-back or 2-back. The total amount of time required for the task is ~12 minutes.

*Functional MRI (fMRI).* Participants will complete measures of neurocognitive function while undergoing fMRI that require a response after the onset of a visual or auditory stimulus. These stimuli may include pictures of alcohol or other beverages, emotional pictures (positive, neutral, negative), and different shapes (e.g. arrows, circles, squares). In addition, we will collect a rest scan, which requires participants to focus on a fixation cross.

*Arterial Spin Labeling Perfusion Sequence (ASL).* Quantification of cerebral blood flow (CBF) will be measured using arterial spin labeling (ASL). Because the BOLD signal may be influenced by CBF in general, we routinely collect ASL (which only adds about 5-7 minutes to the scan time) in order to assess and potentially control for general differences in CBF.

*Structural MRI (sMRI).* We will acquire a high-resolution protocol sufficient to permit accurate tissue classification and anatomical parcellation.

#### Intervention

Participants who meet study criteria will be randomized to active treatment or placebo. The placebo group will receive capsules (filled with microcrystalline cellulose powder) which look identical to capsules filled with active treatment, and will receive the same number of capsules as for active treatment. Members of the study team will be blinded to study randomization; the study pharmacist and/or another honest broker at MRN (e.g. member of the Research Operations team) will be un-blinded, and the pharmacist will not interact with any of the participants. Gemfibrozil will be prescribed at 600 mg by mouth twice daily, *which is the standard FDA approved dose used for the treatment of hypertriglyceridemia*. Adherence will be monitored with bi-weekly pill counts. At the first med dispensing visit (30 minutes, baseline), participants will receive basic information about possible side effects and will be provided with a 2-week supply. During the follow-up med dispensing visit at Visit 5 (15 minutes), individuals will undergo a review of side effects.

All individuals will also receive 4 sessions of motivational enhancement therapy (MET), thus reducing ethical concerns of non-treatment. Therapists will be trained by a MINT-trained trainer.

#### Visit 4

One week after starting medication, participants will complete the second MET session. In addition, participants will complete TLFB, PACS, Helping Alliance Questionnaire, and the CIWA. Expected time: 30 minutes

### Visit 5

Two weeks after starting medication, an additional two weeks of medication will be dispensed, the third MET session will take place, and a follow-up MRI scan (identical to baseline scanning session), blood draw, and assessments will take place. The blood draw will be used to measure LFT's, GGT, and triglyceride levels. Assessments will include the CIWA to measure withdrawal, the ICS to measure impaired control, the PACS to measure craving, the TLFB to measure drinking, the Helping Alliance Questionnaire, and medication side effects. Expected time: MET (30 minutes), MRI (1 hour), Med dispense (30 minutes), Assessments/blood draw (1.5 hours)

### Visit 6

Four weeks after starting medication, the fourth MET session will take place as well as a blood draw and assessments. The blood draw will be used to measure assess LFT's, GGT, and triglyceride levels. Assessments will include the CIWA to measure withdrawal, the ICS to measure impaired control, the PACS to measure craving, the TLFB to measure drinking, the Helping Alliance Questionnaire, and medication side effects. Expected time: MET (30 minutes), Assessments/blood draw (2 hours)

### Phone Call

Six weeks after starting medication, a phone assessment will be used to collect TLFB and PACS data and side effects/other symptoms that may be associated with terminating use of the medication. Expected time: 30 minutes

For all questionnaires listed above, participants may refuse to answer any question at any time. Direct identifiers will be collected and maintained in the MRN COINS database. All data collected as part of this study will be coded with a Unique Research Subject Identifier (URSI).

Instrument/Activity	Screen (Visit 1)	Screen (Visit 2)	Baseline (Visit 3)	Visit 4	Visit 5	Visit 6	Phone Call
Breathalyze	X		X		X		
SCID	X						
TLFB	X		X	X	X	X	X
MRI Screener	X		X		X		
Edinburgh Handedness	X						
Urine Drug Screen	X		X		X		
Pregnancy Test	X		X		X		
Exclusion Criteria List		X					
Medical History		X					
Physical Exam		X					
Blood draw		X			X	X	
PACS			X	X	X	X	X
ICS			X		X		
CIWA			X	X	X		
ADS			X				

FTND			X				
AUDIT			X				
WTAR			X				
DERS			X				
S-DERS			X				
ERQ			X				
PROMIS Anger			X				
PROMIS Depression			X				
PROMIS Anxiety			X				
MCQ			X				
Emotional WM			X				
Digit Span			X				
DRINC			X				
Helping alliance Questionnaire			X	X	X	X	
SoCRArTES			X				
Treatment Services Review			X				
Demographics			X				
Locator			X				
MRI			X		X		
Motivational Enhancement Therapy			X	X	X	X	
Medication Dispensing			X		X		
Medication Dosing Handout			X				
Medication Count				X	X	X	X
SAFETEE/Adverse events				X	X	X	X
Total time (hours)	2	2	4.5	.75	3.5	2.5	.5
Total Payment	\$20	\$20	\$60	\$10	\$80	\$50	\$10

## 11) List of Appendices

ADS.doc  
 AUDIT.doc  
 CIWA-Ar\_101515.docx  
 Demographics\_031218.doc  
 difficultiesinemotionalregulation\_scale.pdf  
 DrInC.pdf  
 Edinburgh\_v09022015.doc  
 ERQ.pdf  
 Fagerstrom Test for Nicotine Dependence (FTND).doc  
 HelpingAllianceQuestionnaire\_paper.pdf  
 ICS-Followup.docx

ICS-Initial.docx  
MCQ\_100115.docx  
MRI Screening Form\_no contrast\_5.7.15.pdf  
Penn Alcohol Craving Scale.doc  
PROMISAnger.pdf  
PROMISAnxiety.pdf  
PROMISDepression.pdf  
SOCRATESv8.pdf  
StateDERS.docx  
TLFB.docx  
Treatment Review Questionnaire\_last 30 days.doc

AdherenceHandoutPatient.docx  
all\_scid.pdf  
Breathalyzer\_UA\_PregnancyResults.doc  
ConcurrentMeds.doc  
DigitSpan.docx  
Exclusion Criteria Checklist Gemfib.docx  
Locator\_030918.doc  
PhoneScreen\_031318.docx  
Physical Exam.doc  
SAE\_initial.pdf  
SAFTEEGemfib.doc  
VitalsBaseline.docx  
WTAR word card.pdf

RecruitmentMaterials\_flyer\_v1.docx  
RecruitmentMaterials\_flyer\_v2.docx  
RecruitmentMaterials\_text\_advertisement\_v031118.docx

gemfibrozilINDexempt.pdf  
gemfibrozil\_patient\_brochure.pdf

## **12) Data and Specimen Banking**

No specimens will be banked as part of this protocol. Participants will be given the option of having their data stored in the MRN Data Repository (see HRRC# 06-387, PI: [name]).

## **13) Data Management**

Consent Forms: Signed consent forms are stored in a locked cabinet in a locked office at MRN.

Questionnaire Data: All data are coded with a unique research subject identifier (URSI) number. Electronic data is stored on a drive only accessible by the research team on a secure MRN server. For non-computer based forms, such as the neuropsychological assessments, the data collection sheets are stored in a locked cabinet in a locked office at MRN.

Behavioral and Imaging Data: All data is coded with the URSI, and collected and stored electronically. Electronic data is stored on a drive only accessible by the research team on a secure MRN server. De-identified data resulting from this study may also be presented at meetings, published in journals/books, used in classrooms for training/teaching purposes, and may be shared with other researchers including scientists at other universities and institutions.

**Study Closure:** At the time of study closure, all participant identifiers (name, address, etc.) will be made inaccessible to the research team. MRN retains the link between identifiers and URSI indefinitely for the potential future benefit to the research participant. Specifically, it may become medically advantageous in the future for a former participant to have access to the clinical information that may be present in radiological scans and reviews. For example, if a participant has been diagnosed with a neurological condition (e.g., multiple sclerosis, glioblastoma, etc.) it may be clinically beneficial for the participant's physician to have access to a research scan that was performed at an earlier time-point to determine disease course and severity.

In addition to the above protections, we have applied for a Certificate of Confidentiality from NIH to further protect subject confidentiality. Upon receipt of the CoC, we will revise the consent to include language that specifies that the investigators have obtained a CoC. Importantly, as stated in the consent, participants are informed that if they report current abuse of a child or an elder, we will report the person to the proper authorities, consistent with New Mexico state law.

**Statistical Analysis:** All MRI data will undergo standard preprocessing (e.g. motion correction, spatial normalization) and quality control prior to statistical modeling. Drinking data and other measures will be analyzed using standard statistical analyses including linear mixed models and the general linear model.

Because the proposed study is a pilot study, we will not likely have sufficient power to detect significant effects. However, we will be able to compute effect sizes for larger trials if the effects look promising.

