## 4) Objectives

In this pilot study, we propose to randomize 20 participants with Alcohol Use Disorder (AUD) to treatment with either placebo or 600 mg of gemfibrozil twice daily for 4 weeks in a **double-blind placebo-controlled, clinical trial**. Participants will receive 4 sessions of motivational enhancement therapy (MET), regardless of medication assignment. Brain responses during response inhibition, stress, and alcohol cue reactivity will be measured with fMRI obtained at baseline and 2 weeks. Triglyceride levels will be obtained at baseline, 2 and 4 weeks. The protocol will be registered on clinicaltrials.gov.

**Aim 1: To investigate the effects of gemfibrozil on alcohol use at 4 weeks in individuals with AUD.** We hypothesize that relative to placebo, gemfibrozil will improve alcohol use outcomes as defined by rate of change in drinks per drinking day (DPDD), drinks per week (DPW) and percent days abstinent (PDA). Effect sizes for all 3 metrics will be calculated to determine if a larger clinical trial is warranted.

**Aim 2: To investigate the effects of gemfibrozil on various possible biological targets which are increasingly recognized as important mechanisms by which treatments for AUD work.** In particular we hypothesize that gemfibrozil will result in 1) increased engagement of cognitive control networks (inferior frontal gyrus (IFG) and dorsal anterior cingulate cortex (ACC)) during response inhibition, 2) decreased response in networks involved in reward (ventral and dorsal striatum, ACC) during the presentation of alcohol cues, 3) decreased response in networks that process negative affect [amygdala, insula, and ventromedial prefrontal cortex (PFC)] in response to emotional pictures, and 4) reduced triglyceride levels. We also hypothesize that changes in these targets will mediate the effects of gemfibrozil on alcohol use at 4 weeks.

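### Aim 1 is framed on rate of change, and no baseline adjustment is specified for either aim, although a pre-treatment value of every outcome is collected

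*Combined protocol and SAP*

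**What the plan says.** Section 4 states the Aim 1 hypothesis for alcohol use outcomes "as defined by rate of change in drinks per drinking day (DPDD"), with drinks per week and percent days abstinent named alongside. The resulting effect sizes are to decide whether a larger trial is justified.

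The Aim 2 outcome hypotheses in Section 4 are directional: more engagement of control networks, less response to alcohol cues and to emotional pictures, lower triglycerides. Only the closing mediation hypothesis speaks of "changes in these targets".

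The modelling text for all of this is in Section 13, Statistical Analysis: "Drinking data and other measures will be analyzed using standard statistical analyses including linear mixed models and the general linear model". It gives no outcome form, covariate or baseline term. The same section concedes that power will probably be inadequate and offers effect sizes as the product.

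Pre-treatment values are available throughout. At screening, "participants will complete a 90 day timeline follow-back (TLFB"). Triglycerides are drawn at screening or at the medical history visit, and the first MRI is done at the baseline visit. On allocation, the Intervention text says only "Participants who meet study criteria will be randomized to active treatment or placebo", with no ratio and no stratification by baseline severity.

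**The concern.** The one concrete statement about the drinking outcome points towards change. In a mixed model its natural reading is a time-by-group term with each arm's baseline mean estimated freely. With one pre-treatment and one follow-up value, that is the change-score contrast. It subtracts the whole of any chance baseline difference, when only the correlated part should be removed, and so over-corrects: the arm that happens to start higher appears to improve more.

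A baseline-adjusted analysis uses data the trial already collects and avoids this. The point matters here because the pilot's output is a set of effect sizes from about 10 people per arm, to be used for a go or no-go decision. If the treatment of baseline is left open, it can also be settled after the data are seen.

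**Working it through.** The plan gives no power figure, alpha, SD or effect size, so it has no figure to reproduce.

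**Inputs from the documents**
- Number randomised: 20. Section 4: "we propose to randomize 20 participants with Alcohol Use Disorder (AUD) to treatment with either placebo or 600 mg of gemfibrozil". Section 9: "The study will close enrollment once 20 participants have been randomized". Section 6 mentions 40 and Section 26 speaks of 20 completers; I use 20 randomised.
- Retention, Section 9: "we expect ~70-80% of participants will complete at least two weeks of the medication". That is 0.70 × 20 = 14 to 0.80 × 20 = 16 people, or 7 to 8 per arm. I use 7 per arm as the lower case for available data.

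**Assumptions, not in the documents:** 1:1 allocation (10 per arm), baseline-to-follow-up correlation r ranged from 0.3 to 0.9, equal SDs at both times, normal data, two-sided 95% intervals. Results are in SD units.

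**Step 1. Precision, one pre and one post value.** With n per arm and N = 2n:
- Change score: half-width = t(N−2) × √[2(1−r) × 2/n].
- Baseline-adjusted: half-width = t(N−3) × √[(1−r²) × (2/n) × (1 + 1/(N−4))]. The last factor is the price of estimating the slope: 1 + 1/16 = 1.06 at N = 20, and 1 + 1/10 = 1.10 at N = 14.

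Example, n = 10, r = 0.5:
- Change: 2.101 × √(1.0 × 0.2) = 0.94.
- Adjusted: 2.110 × √(0.75 × 0.2 × 1.0625) = 0.84.
- Ratio: 1.12.

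| r | 10 per arm: change / adjusted | ratio | 7 per arm: change / adjusted | ratio |
|---|---|---|---|---|
| 0.3 | 1.112 / 0.928 | 1.20 | 1.378 / 1.177 | 1.17 |
| 0.5 | 0.940 / 0.842 | 1.12 | 1.165 / 1.069 | 1.09 |
| 0.7 | 0.728 / 0.695 | 1.05 | 0.902 / 0.881 | 1.02 |
| 0.8 | 0.594 / 0.584 | 1.02 | 0.737 / 0.740 | 0.995 |
| 0.9 | 0.420 / 0.424 | 0.99 | 0.521 / 0.538 | 0.97 |

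Simulation (20,000 trials per setting) agreed. In single trials at 10 per arm, the change-score interval was the wider one in 90%, 80%, 63% and 37% of trials at r = 0.3, 0.5, 0.7 and 0.9.

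**Step 2. Chance imbalance.** The baseline mean difference b has SD √(2/n): 0.447 at n = 10 and 0.535 at n = 7.
- n = 10: P(|b| > 0.5) = 2 × [1 − Φ(0.5/0.447)] = 0.264.
- n = 7: P(|b| > 0.5) = 2 × [1 − Φ(0.5/0.535)] = 0.350.

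Given b, the unadjusted change estimate shifts by −(1−r)b. For b = 0.5 SD the shift is 0.7 × 0.5 = 0.35, 0.5 × 0.5 = 0.25 and 0.3 × 0.5 = 0.15 SD at r = 0.3, 0.5 and 0.7.

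**Step 3. Steps 1 and 2 describe one harm.** Before small-sample corrections, the excess variance of the change score is [2(1−r) − (1−r²)] × 2/n = (1−r)² × 2/n. The variance of the shift (1−r)b is also (1−r)² × 2/n.

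**Step 4. Unequal SDs.** With k = baseline SD / follow-up SD, the large-sample variance ratio of change to adjusted is (1 + k² − 2rk)/(1 − r²). At r = 0.5 it is 0.79/0.75 = 1.05 for k = 0.7, 1.33 for k = 1, and 1.39/0.75 = 1.85 for k = 1.3 (k assumed).

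**The case against.** The strongest reply is that the plan has not chosen a change-score analysis. A general linear model with baseline as covariate, and a mixed model with a common baseline mean, both belong to the classes Section 13 names. That is correct. A reader might infer that the sponsor has committed both aims to unadjusted change; the documents do not support this. Aim 1 has the rate-of-change wording but no estimator. Aim 2 uses change wording only for mediation, so its gap is simply the missing baseline term.

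Three further objections stand in part:
- The timeline follow-back is repeated at Visits 3 to 6 and at the phone call, so the Aim 1 rate may be a slope over several points. The two-point formulas illustrate the size of the problem; no slope calculation has been made.
- Equal SDs are doubtful for drinking, where a 90-day baseline window is set against four weeks of treatment. Step 4 shows the penalty could be much smaller or larger than the equal-SD figure.
- One assumed range of r serves drinking, BOLD response and triglycerides alike.

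None of this makes the silence harmless. Nothing in the plan selects the adjusted model, and the only pointer for drinking leads away from it. A moderate r is plausible for drinking: entry requires recent heavy drinking, all participants receive motivational enhancement therapy, and Section 18 expects people to cut down even without active treatment.

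**Conclusion.** The concern holds in this form: Aim 1 is framed on rate of change, and baseline adjustment is provided for neither aim. The natural unadjusted reading of Aim 1 costs about 5% to 20% in interval width at 10 per arm, and 2% to 17% at 7 per arm, for r from 0.7 down to 0.3. These figures rest on 1:1 allocation, equal SDs and a single pre/post pair.

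Two stronger readings should be resisted. A reader might infer that a change analysis widens every interval. At 14 to 20 participants it does not: the advantage of adjustment is gone just below r = 0.8 at 7 per arm and between 0.8 and 0.9 at 10 per arm, though the reversal at r = 0.9 is only about 1% to 3%. A reader might also count bias as a second harm on top of lost precision. Under randomisation the change estimate is unbiased on average; its distortion is conditional on the imbalance that occurs, and Step 3 shows this is the same quantity.

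The plan should be changed on this point, because the estimates are meant to decide on a larger trial and the better method is nearly free.

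**What to change.** Add two sentences to Section 13, Statistical Analysis:

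*Each outcome's follow-up values will be compared between arms with that outcome's own pre-treatment value as covariate, or in a linear mixed model in which the arms share a common baseline mean. Effect sizes will be reported with confidence intervals from that model.*

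The sponsor should choose one of the two forms before unblinding and name the baseline value for each outcome:
- Drinking: the same metric computed from the pre-treatment timeline follow-back days.
- Each BOLD region: the baseline-scan value.
- Triglycerides: the baseline level. A log scale at both times is optional; the documents do not call for it.

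The rate-of-change wording in Section 4 should then be aligned with this.

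Cost: no new data or visits. The covariate form uses one degree of freedom (t critical value 2.101 to 2.110 with 20 participants, 2.179 to 2.201 with 14) and adds about 6% to the variance at N = 20, or 10% at N = 14, for estimating the slope. Both are already in the half-widths above.
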